### 9.2 Safety Endpoints

The following safety data will be collected according to the study protocol.

- Adverse event
- Laboratory test data
- Vital signs data
- 12-Lead ECG
- ECOG PS
- Physical examination

### 9.3 Other Endpoints

Not applicable.

### 9.4 Covariates

Not applicable.

## 9.5 Analysis Window

Data obtained from post-baseline visits will be summarized by protocol visits shown in eCRF, with no need to consider whether the visit window specified by the protocol has been exceeded.

When a planned visit is missing, or one of the test items in the planned visit is missing or its results are invalid, the unplanned visit closest to the planned visit will be considered as the protocol visit. If the time of two unplanned visits is equally close to the time of planned visit, the later unplanned visit will be selected as the protocol visit. All visits in the protocol will be sorted in chronological order. In addition, once defined as a protocol visit, an unplanned visit will no longer be defined as other protocol visits. In the analysis carried out by visits, the statistical analysis will be performed according to the planned time points in the protocol, i.e., the time points of unplanned visits do not need to be shown.

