6.2 Treatment Period/Follow-Up

The treatment period starts from the subject's first dose. The first dose of the study drugs should be given as close as possible to the time of completing the screening examinations and confirming the subjects' eligibility for the study. Each treatment cycle lasts for 21 days.

All examinations and evaluations (except for imaging evaluations) should be completed within 3 days pre-administration. There is no need to repeat the laboratory tests (hematology, urinalysis, blood biochemistry, coagulation function test, and thyroid function test) and electrocardiography on Day 1 of Cycle 1, if such tests have already been performed at the baseline within 7 days before the first dose.

- ◆ For subjects receiving the SHR-1210 + apatinib treatment for the first time, blood samples should be collected for PK and immunogenicity testing. The specific procedures can be found in the schedule of activities or section 3.1 "Pharmacokinetic and Immunogenicity Studies" in the protocol.
- ◆ The following evaluations should be completed before the drug administration in each cycle:
 - ECOG PS
 - Vital signs
 - Physical examination: Specific physical examination is performed if clinically indicated.
 - Hematology
 - Clinical chemistry
 - Coagulation function
 - 12-Lead ECG
 - Collection of AEs
 - Documentation of concomitant medications/concomitant treatments
- ◆ The following evaluations should be completed every 2 cycles prior to administration:
 - Urinalysis
 - Thyroid function
 - Fecal occult blood

- ◆ Imaging examination: Imaging examination is performed once every 2 cycles (6 weeks ± 7 days) in the first 12 months (the first 16 cycles), then once every 3 cycles (9 weeks ± 7 days). Imaging examination should be also performed if new lesions are suspected. Imaging examination should be performed when subjects withdraw from the study for any reason (the imaging examination does not need to be repeated if the time from the last examination is no more than 4 weeks). Imaging conditions should be the same as those at baseline (including slice thickness and contrast agent). The time window for imaging examination is ± 7 days. Unscheduled imaging examination may be performed if PD is suspected (for example, worsening of symptoms). The date of imaging examination is calculated by the calendar day and will not be adjusted due to dose delays.

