6.5 Unscheduled Visit

The following shall be documented during unscheduled visits when subjects develop AEs during the study:

- Concomitant medications/treatments;
- Adverse events;
- All relevant examinations (including imaging evaluations, if any).

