## 10.2 Handling of Missing Data of Safety Evaluation

Unless otherwise specified, missing safety endpoint values will not be imputed. Please refer to Appendix 1.4 for the imputing of date/time of adverse events and concomitant medications.

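### SAP 9.5 lets an unplanned value stand in for a missed Day 1 safety assessment with no limit on distance, cycle or timing relative to the dose

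*SAP*

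**What the plan says.** SAP 9.5 has two parts. The first assigns post-baseline data to the protocol visits recorded in the eCRF, "with no need to consider whether the visit window specified by the protocol has been exceeded". The second deals with gaps. It applies "When a planned visit is missing, or one of the test items in the planned visit is missing or its results are invalid", and then "the unplanned visit closest to the planned visit will be considered as the protocol visit".

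The section adds four details:
- Ties go forward in time: "If the time of two unplanned visits is equally close to the time of planned visit, the later unplanned visit will be selected".
- Each unplanned visit has a single use: "once defined as a protocol visit, an unplanned visit will no longer be defined as other protocol visits".
- Visits are to be put in chronological order, without saying whether this restricts the choice of substitute or only the layout of the output.
- By-visit analyses use the planned time points, so the time of an unplanned visit need not appear.

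On the planned assessments, Protocol 6.2 says: "All examinations and evaluations (except for imaging evaluations) should be completed within 3 days pre-administration". The Schedule of Activities heads these columns D1 ± 3, and cycles last 21 days. On unscheduled visits, Protocol 6.5 says: "The following shall be documented during unscheduled visits when subjects develop AEs during the study". A note under the Schedule of Activities also lets the investigator add visits when needed. SAP 10.2 says: "Unless otherwise specified, missing safety endpoint values will not be imputed".

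**The concern.** A planned laboratory, vital-sign or ECG value is a pre-dose value at the start of a cycle. An unplanned value can come from any day of any cycle. The two are not interchangeable. In the chemotherapy phase of cohort 1, capecitabine is given on Days 1 to 14 and stopped on Days 15 to 21, so a Day 1 value from Cycle 2 on follows a planned rest week and a mid-cycle value does not.

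Laboratory abnormalities, vital signs and ECG are named secondary endpoints (Protocol 2.2). SAP 11.4.2 summarises laboratory values, change from baseline and normal/abnormal change by visit. SAP 11.4.3 summarises vital signs by visit, and SAP 11.4.5 summarises ECG at each time point. At stake is the time course of toxicity that these tables are meant to show, most of all at late visits where few subjects remain. Because the substitute's own time need not be shown, a reader of the table could not tell that a substitution had been made.

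**Working it through.** The plan states no figure to reproduce here. The check sets the rule against the visit schedule and then illustrates the distances.

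**1. Visit days.** With 21-day cycles and no delays, Cycle n Day d falls on study day 21 × (n − 1) + d.
- C9D1 = 21 × 8 + 1 = day 169
- C9D2 = 21 × 8 + 2 = day 170
- C10D1 = 21 × 9 + 1 = day 190
- C11D1 = 21 × 10 + 1 = day 211

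**2. What the rule tests.**

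| Condition on the substitute | Stated in SAP 9.5? |
|---|---|
| Closest in time | Yes |
| Not already used for another visit | Yes |
| Maximum distance | No |
| Same cycle | No |
| Before that cycle's dose | No |
| Chronological order | Mentioned; effect on selection unclear |

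**3. Strict reading of chronological order.** Suppose a substitute must lie between the neighbouring planned visits. A subject has no valid C10D1 laboratory test, and the only unused unplanned visit is on C9D2. Day 170 lies between days 169 and 211, so the value is in order and is tabulated as C10D1. It is 190 − 170 = 20 days early, in the previous cycle and one day after a dose. The same happens in the chemotherapy phase: C3D2 (21 × 2 + 2 = day 44) can stand for C4D1 (21 × 3 + 1 = day 64), again 20 days apart.

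Urinalysis is planned every two cycles, so its neighbouring planned tests are 42 days apart. An in-order substitute can then be up to 41 days away.

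**4. Tie rule.** If the two nearest unplanned visits are on days 186 and 194, each is 4 days from day 190. The later one is chosen. Day 194 is C10D5, which is after the dose if C10D1 dosing took place.

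**5. How far away substitutes would tend to lie (illustration).** The documents give no frequency or timing of unplanned visits. With one unplanned visit placed uniformly between neighbours 21 days either side:
- within 3 days: 6 / 42 = 14%
- more than 10.5 days away: 21 / 42 = 50%

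A simulation assumed 6, 8 or 12 cycles, 1, 2 or 4 unplanned visits per subject and uniform timing:

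| Reading of chronological order | Within 3 days | More than 10.5 days | More than 21 days |
|---|---|---|---|
| Substitute must lie between neighbours | 14–22% | 36–50% | 0% |
| Display order only | 2–18% | 48–92% | 20–83% |

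Under either reading, a large share of substitutes would lie nearer to another Day 1 than to the one they represent.

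**The case against.** The strongest defence is the sentence on chronological order. If it restricts selection, the substitute normally stays less than 21 days away for a test done every cycle. A reader might infer that the rule can place a C2D8 value (day 29) at C10D1 (day 190), 161 days away. In a subject with intervening visits that would break the order SAP 9.5 asks for, so the text does not clearly support it. It follows only if the sentence means display order. The 20-day example survives either way.

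Four other points are fair:
- The sentence on disregarding visit windows concerns data recorded under planned visits. It is not itself the substitution rule. It does mean that no protocol window is carried into the section.
- A reader might see a contradiction with SAP 10.2. There is none: 10.2 allows exceptions, 9.5 acts as one, and the rule reassigns an observed value. What is missing is a cross-reference.
- A reader might infer that most substitutes are abnormal values taken because of an adverse event. Protocol 6.5 makes some such values likely, but investigators may add visits for other reasons, no document gives a share, and an adverse-event visit need not yield an abnormal laboratory, vital-sign or ECG value.
- A reader might assume that by-visit normal/abnormal shifts are affected throughout. Only laboratory tests have them. The ECG normal/abnormal summary compares before with after treatment, and vital signs have no such table.

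**Conclusion.** The point stands in a limited form. Applied as written, SAP 9.5 can put values from the previous cycle, or from after dosing, into by-visit cells that represent a pre-dose Day 1 assessment, without any visible sign. For tests done every cycle the misplacement can reach 20 days on the strict reading of chronological order. For urinalysis it can reach 41 days. If the order sentence governs display only, it can be much more.

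The effect is confined to descriptive by-visit safety summaries, including the by-visit normal/abnormal change for laboratory tests. ORR and the two-stage decisions do not use the rule. Adverse-event incidence comes from adverse-event records, and the laboratory, vital-sign and ECG listings are still produced.

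The day counts assume undelayed 21-day cycles. The percentages rest on assumed numbers and timing of unplanned visits and show only that distant substitutes would not be rare. How many cells would be affected in this trial cannot be derived from the documents.

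**What to change.** In SAP 9.5, accept an unplanned value for a planned assessment only if both conditions hold:
- It lies no further from the planned date than the midpoint to the adjacent planned assessment of that same test. This is about 10 days for tests done every cycle (21 / 2 = 10.5) and about 21 days for urinalysis done every two cycles (42 / 2 = 21).
- Where that cycle's dose was given, it was taken before that dose.

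Otherwise leave the by-visit cell missing. State whether chronological order restricts selection or only display. State that unplanned values still count in the normal/abnormal summaries comparing before with after treatment, and that they appear in the listings, so that no toxicity is lost. Add a cross-reference to 9.5 in SAP 10.2.

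The cost is a few lines of SAP text, the matching programming conditions, and a smaller n in some by-visit cells. The SAP is to be finalised before database lock, so the wording belongs in that version. The limit narrows the problem without removing it: 10 days before C10D1 is day 180, which is C9D12, so some mid-cycle values would still qualify.

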# 10 HANDLING OF MISSING VALUES

## 10.1 Handling of Missing Data of Tumor Assessment

When missing, the tumor assessment data will be treated according to RECIST (v1.1, refer to the table in appendix for details).

## 10.2 Handling of Missing Data of Safety Evaluation

Unless otherwise specified, missing safety endpoint values will not be imputed. Please refer to Appendix 1.4 for the imputing of date/time of adverse events and concomitant medications.

## 10.3 Handling of Missing Data of Tumor Biomarkers

Missing tumor biomarker data will not be imputed.

# 11 STATISTICAL ANALYSIS

The statistical analysis involved in this study will be carried out in accordance with cohorts. The statistical analysis plan must be finalized before database locking. Statistical tables, listings, and figures will be generated using SAS (v9.4).

In this study, unless otherwise stated, all data will be summarized using descriptive statistics in accordance with the following general principles.

Measurement data will be summarized by mean, standard deviation, median, maximum, and minimum. The decimal places of minimum and maximum should be consistent with those recorded on the CRF, mean and median have one more decimal place than those of the raw data, and the standard deviation has 2 more decimal places than that of the raw data. Count data will be summarized by frequency and percentage; categorical variables will be statistically described using the frequency and percentage of each category, with one decimal place rounded for percentages.

Time-to-event data will adopt the Kaplan-Meier method to estimate survival rates and plot survival curves; serum concentration data will be summarized using geometric mean, geometric standard deviation, geometric coefficient of variation, mean, standard deviation, coefficient of variation, median, maximum, and minimum.

## **11.1 Subject Distribution**

The reasons for screening failure will be summarized by frequency and percentage, and the percentage will be calculated using the number of subjects subjected to screening as the denominator.

All enrolled subjects will be divided into cohorts and summarized by frequency and percentage. In addition, as for subject distribution, the following information will be summarized by frequency and percentage for cohorts:

- Number of subjects enrolled;
- Number of subjects withdrawn from the study;
- Number of subjects whose study is underway;
- Reason for treatment discontinuation;
- Reason for subject withdrawal after the end of study;

The percentages will be calculated using the number of all enrolled subjects as the denominator. In addition, the corresponding listing of subjects will be provided.

## **11.2 Demographics and Other Disease Characteristics**

This analysis will be carried out based on FAS.

### **11.2.1 Demographics**

Demographics (age, gender, ethnicity, height, body weight, BMI [kg/m^2]) and ECOG PS will be summarized and listed by cohort. The calculation of age (years) is based on the date of signing of the informed consent form and the date of birth.

The BMI calculation formula is: Baseline body weight (kg)/baseline height (m^2).

### **11.2.2 Tumor diagnosis**

The descriptive statistics of baseline disease characteristics will be provided by cohort.

### **11.2.3 History of drug allergy**

The descriptive statistics of allergy history data will be provided and listed by cohort.

#### **11.2.4 Medical history**

The descriptive statistics of medical history data will be provided and listed by cohort.

#### **11.2.5 History of concomitant diseases**

The descriptive statistics of medical history data will be provided and listed by cohort.

#### **11.2.6 Tumor treatment history**

The frequency and percentage of subjects with history of tumor surgery, history of radiotherapy, history of neoadjuvant chemotherapy, history of adjuvant chemotherapy, and other tumor treatment history will be summarized.

#### **11.2.7 Medication history and concomitant medication**

Prior medications are defined as drugs whose use has been completed before the first dose of the investigational drug during the treatment period. Concomitant medications are defined as drugs that are used after the first dose of the investigational drug, or drugs that are used before the first dose of the investigational drug but are continued to be used during the treatment period.

Medication history and concomitant medications will be descriptively summarized and listed by cohort.

### **11.3 Drug Compliance**

The descriptive statistics of the exposure time, amount of exposure, number of treatment cycle, frequency of dose interruption, frequency and reason of dose discontinuation, frequency and reason of dose delay, final dosage, and reason for dose modification of study drugs (SHR-1210, oxaliplatin, apatinib, and capecitabine) will be summarized by cohort. In this study, SHR-1210 and oxaliplatin will be administered via intravenous drip infusion. The amount of apatinib and capecitabine dispensed and returned at each visit will be counted by tablet. The strength of apatinib is 375 mg/tablet and 250 mg/tablet, and that of capecitabine is 500 mg/tablet and 150 mg/tablet.

1) Actual cumulative drug exposure (mg)

#### **SHR-1210:**

Dose per cycle in study =  $200 \text{ mg} \times \text{Actual dosing percentage (\%)}$

#### **Oxaliplatin:**

Dose per cycle in study =  $\text{Total dose of this dosing (mg)} \times \text{Actual dosing percentage (\%)}$

#### **Apatinib:**

Dose per cycle in study =  $\text{Total daily actual dose} \times \text{Number of days the corresponding dose is used (days)}$

**Capecitabine:**

Actual dose per cycle = Total daily actual dose  $\times$  Number of days the corresponding dose is used (days) = Total daily dose  $\times$  (Start date - End date + 1)

2) Scheduled dose (mg)

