5.1.5 Administration of study drugs

SHR-1210

SHR-1210, intravenous infusion at a fixed dose of 200 mg over 30 min (the total infusion time should be no less than 20 min and no more than 60 minutes, including rinsing period), once every 3 weeks.

Apatinib Mesylate Tablets

375 mg, administered orally once daily. Administered with warm water approximately half an hour after meals (administration time should be the same in each day whenever possible).

Capecitabine

1000 mg/m², administered orally twice daily 30 min after meals (once in the morning and once in the evening; with a total daily dose of 2000 mg/m²). Two weeks of treatment is followed by 1 week of rest period (i.e., drug administration from Day 1 to Day 14, and drug interruption from Day 15 to Day 21) in 3 week cycle.

Oxaliplatin

130 mg/m², intravenous infusion with 250-500 mL of 5% glucose solution, given over 2-6 h; administered on Day 1 of each treatment cycle, once every 3 weeks.

SHR-1210 will be administered intravenously followed by oxaliplatin at least 30 min interval on Day 1 of each cycle.

Study Treatment	Drug	Treatment Cycle (21 days)	
Cohort 1	SHR-1210 200 mg	Day 1	
	Capecitabine 1000 mg/m ²	Day 1-Day 14	4-6 cycles
	Oxaliplatin 130 mg/m ²	Day 1	
	SHR-1210 200 mg	Day 1	
	Apatinib 375 mg	Day 1-Day 21	
Cohort 2	SHR-1210 200 mg	Day 1	
	Apatinib 375 mg	Day 1-Day 21	

Table 6. Administration plan of the study drugs

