**Apatinib:**

Scheduled dose per cycle = Total dose of this dosing (mg)

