**Capecitabine:**

Scheduled dose per cycle = Total daily scheduled dose  $\times$  Number of days the corresponding dose is used (days)

3) Subject compliance (%) = (Actual dose/Scheduled dose)  $\times$  100%.

All study drugs will be listed and analyzed by cohort, subject code, treatment stage, dosing date, and actual dose.

4) Duration of exposure to study drugs (weeks) = (Date of last dosing - Date of first dose + 1)/7.

Actual dose, scheduled dose, and compliance will be summarized by drug and cohort.

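### SAP 11.3: the capecitabine day count is reversed, and the scheduled-dose denominators for apatinib, capecitabine and oxaliplatin are incomplete or cancel with the numerator

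*SAP*

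**What the plan says.** SAP 11.3 (Drug Compliance) defines compliance as actual dose divided by scheduled dose, times 100%, and commits to reporting actual dose, scheduled dose and compliance by drug and cohort. Its formulas are as follows.

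- **Capecitabine, actual dose.** One line gives two expressions as equal: daily actual dose times days used, and daily dose times "Start date - End date + 1".
- **Capecitabine, scheduled dose.** "Scheduled dose per cycle = Total daily scheduled dose", multiplied by the same days-used phrase as the actual dose.
- **Apatinib, actual dose.** Daily actual dose times "Number of days the corresponding dose is used (days").
- **Apatinib, scheduled dose.** "Scheduled dose per cycle = Total dose of this dosing (mg"), with no number of days. The once-per-cycle oxaliplatin infusion has the same wording.
- **Oxaliplatin.** The total for the administration is the scheduled dose. That same total, times the percentage actually given, is the actual dose.
- **SHR-1210.** A fixed 200 mg per cycle is the scheduled dose; 200 mg times the percentage given is the actual dose.

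The regimen comes from Protocol 5.1.5. Capecitabine is given "with a total daily dose of 2000 mg/m²", with "drug administration from Day 1 to Day 14, and drug interruption from Day 15 to Day 21". Apatinib is "375 mg, administered orally once daily". Protocol 6.2 adds: "Each treatment cycle lasts for 21 days".

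**The concern.** These formulas define planned outputs, so each should return 100% for a subject who takes everything as planned and less for one who does not. The capecitabine date expression and, on one reading, the apatinib ratio fail the first test. The capecitabine ratio, on its natural reading, fails the second for missed days. The oxaliplatin ratio does not register a lower dose level.

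Dose delivery matters in this trial. Protocol Version 6.0 lowered apatinib from 500 to 375 mg/d on tolerability grounds, and readers will use the exposure tables to judge how much of each drug was received. Only SHR-1210 has an explicit fixed reference, so the percentages would not be comparable across the four drugs.

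**Working it through.** The SAP states no compliance figure to reproduce. The check puts the protocol regimen into the SAP formulas.

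**Inputs.** Capecitabine 2000 mg/m² per day on Days 1 to 14, apatinib 375 mg per day on Days 1 to 21, and oxaliplatin 130 mg/m² on Day 1 (Protocol 5.1.5). Oxaliplatin reductions are to 75% or 50% of the initial dose (Protocol 5.2.2).

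**Capecitabine, actual dose**
- First expression: 2000 × 14 = 28,000 mg/m².
- Date expression as printed: 1 - 14 + 1 = -12 days, so 2000 × (-12) = -24,000 mg/m². Against 28,000 planned, that is -85.7%.
- The printed expression is right only for a one-day course (1 - 1 + 1 = 1). It gives 0 for two days and a negative value from three days on.
- The two halves of the SAP line therefore disagree: 14 days against -12.

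**Capecitabine, compliance by the first expression**
- 10 of 14 planned days at full dose, with days used in both places: (2000 × 10) / (2000 × 10) = 100%.
- Against planned days: (2000 × 10) / (2000 × 14) = 71.4%.
- Daily dose reduced to 1500, scheduled daily dose kept at 2000, 14 days: (1500 × 14) / (2000 × 14) = 75%. Daily-dose reductions still show on that assumption.

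**Apatinib, compliance**

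| Days taken at 375 mg | Actual dose | Denominator is one daily dose (375 mg) | Denominator is planned cycle total (375 × 21 = 7,875 mg) |
|---|---|---|---|
| 21 | 7,875 mg | 2100% | 100% |
| 14 | 5,250 mg | 1400% | 66.7% |

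The SAP does not say which denominator is meant.

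**Oxaliplatin, compliance**
- The total cancels: (total × percentage given) / total = percentage given.
- Full infusion at the 75% level: 97.5 / 97.5 = 100%. Against the starting dose: 97.5 / 130 = 75%.
- Full infusion at the 50% level: 65 / 65 = 100%. Against the starting dose: 65 / 130 = 50%.
- Infusion stopped at 80%: 80%, so a partial infusion does show.

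**SHR-1210.** (200 × percentage given) / 200 = percentage given. This is sound within a cycle, because the dose is fixed.

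**The case against.** Several parts of the defence have force.

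- **The reversed dates look like a slip.** The same line first gives the right quantity, and the exposure-duration formula later in SAP 11.3 has the right order (last minus first, plus one). A negative dose would probably be noticed in programming. This stands as a reason to call the error easy to repair, not as a reason to leave it in.
- **The 2100% depends on one reading.** The left side of the apatinib formula speaks of a dose per cycle, so a cycle total may be intended. This stands. But the oxaliplatin wording is reused for a once-daily drug, and the text does not settle the point.
- **The capecitabine phrase could mean scheduled days.** It sits under the scheduled-dose heading, and on that reading 10 of 14 days gives 71%. This is possible, but the identical phrase in the actual dose means days used, so the natural reading makes the days cancel.
- **Oxaliplatin may be a choice.** A subject who receives a protocol-directed reduced dose in full has complied with the prescription. This largely stands: compliance and relative dose intensity are different measures, and the SAP needs to say which one it reports.

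A reader might go further and infer that the exposure table cannot show real dose delivery at all, that compliance is automatically 100%, or that missed apatinib days are hidden. The documents do not support this. SAP 11.3 separately summarises exposure time and amount, cycles, interruptions, delays, discontinuations, final dose and reasons for modification. Partial oxaliplatin infusions and lower capecitabine daily doses still move the percentage. Missed apatinib days lower it on either reading in the table above.

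**Conclusion.** The point holds in a limited form. The capecitabine date expression is wrong as printed (-12 days for 14) and corrupts both actual exposure and compliance if used. The apatinib denominator is ambiguous by a factor of 21 for a full cycle. The capecitabine denominator, on its natural reading, hides missed days (100% instead of 71% for 10 of 14). The oxaliplatin denominator does not show reductions to 75% or 50%; that is a defect only if the percentage is meant to reflect dose intensity.

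The effect is confined to the actual-dose, scheduled-dose and compliance summaries for these drugs. SHR-1210 within a cycle is unaffected, as are the separate summaries of interruptions, delays and modifications. ORR and the two-stage decision rule do not use these quantities. The size of the error rests on literal programming and on the readings stated; the SAP's other expressions would let a careful programmer recover part of the intent. This merits correction but does not threaten the primary result.

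**What to change.** Amend SAP 11.3 as follows.

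1. Replace the capecitabine day count with (End date - Start date + 1), applied to each continuous run of dosing so that interruption days inside a record are not counted as taken.
2. Define scheduled dose per cycle as scheduled daily dose times protocol-planned days: 21 for apatinib, 14 for capecitabine.
3. State a rule for cycles cut short by discontinuation. Without one, a subject who stops apatinib after Day 8 for progression would score 8 / 21 = 38%, which is not non-compliance.
4. State whether the percentage is compliance with the prescribed dose or relative dose intensity against the subject's protocol starting dose. Report relative dose intensity as a separate line, so that reductions are visible for oxaliplatin and the oral drugs. For apatinib, take each subject's own starting dose, since subjects were treated at 500 mg/d before Version 6.0.

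These are analysis definitions only and change no dosing rule. The cost is SAP wording and programming; no new data collection is implied, since SAP 11.3 already plans to list dosing dates and actual doses. Values can move either way: the negative capecitabine figures rise, while cycles with missed days fall.
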